This is a before and after methodological approach, which will involve collection of baseline data over 12 months, followed by staged implementation. Implementation will take place over two phases: a sandbox, or virtual implementation of the system (referral decisions made by GDPs will be captured, however all patients will ultimately be treated in secondary care) followed by full implementation of the system, (appropriately referred patients being treated in both primary and secondary care settings).

The pilot study suggests that changes in referral behaviour can be detected as early as three months following the introduction of a management system. The cost reductions seen by triage diversion are seen immediately. However, in order to understand the long-term implications of the referral system, including any reactive behaviour by GDPs or Secondary Care providers we are proposing to run the introduction of the system for 12 months and the full diversion service for a further 12 months. This should allow a full financial year's worth of cost data to be assessed as well as determining the degree of adaptation to the system. The time period will also enable a robust assessment of primary care treatment quality – i.e. there will be sufficient time to determine if cases treated in primary care return to secondary care for additional or remedial treatment as well as tracking seasonal variations in

Version 2 15 September 2015

referrals. For example we have noted decreases in referral volumes around December and January (relating to the holiday period) and increases in volumes round March (relating to end of financial year).

Implementation 1: Virtual Referral management without diversion (year 2)

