The quantitative analysis has been designed to evaluate the impact of a change in service, with the primary analysis using a piecewise regression / interrupted time series analysis (ITS) design. This is an appropriate methodology to evaluate the effects of a change in service delivery. Whilst it is acknowledged that the lack of a concurrent control group can be considered a weakness (Brown & Lilford, 2008), the nature of the investigation and implementation precludes such a design. The proposed study design and analysis will aim to minimize threats to internal validity (Ramsay et al, 2003): A single PCT boundary (NHS Sefton) with a diverse practice and patient profile has been identified for study; lengthy evaluation pre-intervention and during two stage implementation over three years will address any concerns regarding secular trends (Brown & Lilford, 2009). Additionally, trends observed in Sefton over the implementation period with be compared with national trends in oral surgery referrals through the examination of Hospital Episode Statistics (HES) data. This design will enable 24 months of referral management assessment during the study, and thus captures and enables the measurement of seasonal variations in referral patterns. Further, a large intervention effect has been observed in an earlier pilot study, with a re-direction of MOS referrals from secondary care to primary care based services of over 68% (data from Central Manchester Foundation Trust). The primary outcome measures will be the monthly reported number and ultimate destination of referrals from baseline through to six months, implementation stage 1 referral management alone (12 to 24 months) and Implementation stage 2, referral management with diversion (24 to 36 months). Analysing monthly data has a number of advantages: it enables the cyclical nature of referrals observed in the pilot study to be accounted for; will illustrate whether referral management alone (the process of collecting, assessing and administratively triaging referrals in the absence of diversion) results in a decrease in referrals into secondary care; short-term changes will not be missed; any observed effect is maintained or return returns to original levels. The principal analysis will be to determine whether the implementation of the Referral Management System with diversion has an effect that is significantly different from any underlying secular trend.

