Statistical analysis will be undertaken using time series regression models. Pre-intervention and post-intervention (virtual and actual implementation) trends will be evaluated. In addition, the pre and post intervention effects at Sefton will be compared with national trends in order to further investigate the effects of possible secular trends. Analysis and reporting will be undertaken according to recommended quality criteria (Ramsay et al, 2003). The best fit pre intervention and post intervention lines will be estimated using linear regression and autocorrelation will be adjusted for by using the maximum likelihood methods where appropriate (Draper & Smith 1981). First order autocorrelations will be tested for statistically using the Durbin – Watson statistic and higher – order autocorrelations will be investigated using the autocorrelation and partial autocorrelation function.

Two effect sizes will be estimated. First, a change in level of outcome at the first point of after the introduction of the intervention will be estimated for each of the referral outcomes (Primary Care, Secondary care, DWSPI, rejected). This will be carried out by extrapolating the pre intervention regression line to the first post intervention point. The difference between this extrapolated point and the post intervention regression estimate for the same point will represent the estimated change in level of referrals. Secondly, a change in the slopes of regression lines will be investigated by calculating the post intervention minus pre intervention slope. The difference observed for each change will be further investigated for statistical significance.

Data will also be presented descriptively and graphically on the number and nature of referrals according to the referral destinations of rejected, primary care, primary advanced or secondary care.

Version 2 15 September 2015

Any trends observed for referrals to secondary care for Sefton will be compared with national trends using Hospital Episode Statistics (HES), which will be obtained via NHS Sefton and analysed for statistical significance at each recorded time point.

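### Adding each month's working days to the segmented regression would cheaply recover precision lost by fitting lines to raw monthly referral counts, mainly for the comparison of referral management alone

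*Protocol*

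**What the plan says.** Section XI of the Protocol, under Quantitative data analysis, fixes the series: "The primary outcome measures will be the monthly reported number and ultimate destination of referrals". The model follows: "The best fit pre intervention and post intervention lines will be estimated using linear regression", with adjustment for autocorrelation where needed. For the level change at the first point after each introduction, the section says: "This will be carried out by extrapolating the pre intervention regression line to the first post intervention point". The extrapolated value is then compared with the post-intervention line at the same point, for each referral destination.

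The section gives as one reason for monthly data that "it enables the cyclical nature of referrals observed in the pilot study to be accounted for", without naming a term that would do so. Section IX, under Interrupted time series study, reports lower volumes around December and January, which it links to holidays, and higher volumes around March, which it links to the financial year end. The same part describes "collection of baseline data over 12 months, followed by staged implementation". No working-day denominator, offset or covariate is mentioned, and none is excluded.

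**The concern.** A calendar month is not a constant unit of exposure. Dental practices and hospital receipt centres can be expected to work mainly on weekdays, and the Protocol itself ties a fall in volume to holidays. The number of working days in a month is known in advance without error. For a given calendar month it also changes from year to year, because weekdays shift and some public holidays move, so a fixed seasonal pattern cannot absorb all of it.

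Whatever is not modelled goes into the residual. With 12-point segments and a level change read off the end of an extrapolated line, residual noise is costly. The comparison at stake is Implementation 1, where section XI asks whether referral management without diversion reduces referrals into secondary care. An effect there may be modest. The only comparable figure in the Protocol is a 9% reduction, given in the Introduction for NHS Manchester.

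**Working it through.** The Protocol states no monthly volume, SD, power or significance level for the time series, so there is no figure of its own to reproduce.

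**Inputs.** From the Protocol: 36 monthly points, breaks at months 12 and 24, and a separate line in each segment. Section XI words the baseline as running to six months; the 12-month baseline of section IX is used here. Assumed: Monday to Friday less English public holidays, 2010–2019; referrals proportional to working days; 100, 200 or 400 referrals a month.

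**1. Working days.** Months hold 18 to 23, with a mean of about 21.1 and a CV of about 5.4%.

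**2. Effect on the fitted lines.** The working-day index (days divided by mean) was fitted with the segmented model over 60 start months, 2011–2015. The residual SD (30 df) averages about 5.5% of the mean. The stage-1 level change produced by the calendar alone averages close to zero, with a mean absolute value of about 4% and extremes of about −10% and +10%. For January, April, September or October starts in 2012–2015, the stage-1 and stage-2 shifts lie between −4.2% and +3.9%.

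This agrees with theory. With times numbered 0 to 11 in each segment, the variance of the level change in units of the residual variance is

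[1/12 + (12 − 5.5)²/143] + [1/12 + 5.5²/143] = 0.379 + 0.295 = 0.674,

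so its SD is √0.674 = 0.82 residual SDs, and 0.82 × 5.5% = 4.5%.

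**3. Precision.** With Poisson CV² = 10,000/volume (in %²) and extra month-to-month CV c, the proportional cut in standard error is 1 − √[(CV² + c²)/(CV² + c² + 5.5²)], where 5.5² = 30.25.

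| Referrals a month | Poisson only | Extra CV 10% |
|---|---|---|
| 100 | 1 − √(100/130.25) = 12% | 1 − √(200/230.25) = 7% |
| 200 | 1 − √(50/80.25) = 21% | 1 − √(150/180.25) = 9% |
| 400 | 1 − √(25/55.25) = 33% | 1 − √(125/155.25) = 10% |

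Simulation (6,000 series per case) agrees. With Poisson noise only, the standard error of the stage-1 level change on raw counts against counts per working day is 9.3% v 8.1%, 7.3% v 5.8% and 6.1% v 4.1% of the mean at the three volumes.

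**4. Error rate and power.** At volumes of 50 to 400 and extra CV of 0, 5 or 10%, type I error at the 5% level is 4.5–6.3% on raw counts and 4.4–5.7% per working day. Power for an illustrative 9% stage-1 fall goes from 15% to 17% (100 a month, 5% extra CV), from 21% to 26% (200 a month, 5% extra) or from 32% to 59% (400 a month, Poisson only). Power for a 68% diversion effect is about 100% either way.

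**5. Cost of estimating the coefficient.** Adding working days as a fitted covariate raises the standard error by about 2% on average for a given residual SD.

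**The case against.** The strongest reply is that this is a modelling refinement of the kind a statistical analysis plan normally settles. The Protocol says nothing false here and excludes no such term. That stands, so the point is offered as an improvement to the stated method and not as an error or contradiction.

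Four stronger readings are tempting, and none is supported.

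- *Raw counts create false effects.* A reader might infer this from the ±10% extremes. The shift averages near zero over start dates, and the wider standard error already covers it. The level shift and the inflated error are largely one effect and should not be counted twice.
- *Working days explain the seasonality.* January averages 21.1 working days, the same as the overall mean, and March 21.7, only about 3% more. Neither the January dip nor the March rise, which the Protocol ties to the year end, is accounted for. Seasonal terms remain necessary.
- *The 9% is the expected stage-1 effect.* It comes from another area, covers all dental specialties, and arose in a scheme that also diverted patients. It serves here only as a scale.
- *The outcome should become a rate.* The outcome is defined as a number, and referral activity also feeds the activity-loss and cost-per-referral work, so replacing it would have a price.

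It is also fair to say that the larger gains need high volume and little extra variation, neither of which the Protocol states, and that power for a 9% fall stays low in several cases with or without the change. Whether the recorded month in the receipt-centre, payment and practitioner-reporting data follows weekday working is unknown.

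**Conclusion.** The point holds as a low-cost gain in precision. If referrals follow working days, the stated method leaves a known component of about 5.5% of the mean in the residual SD. Removing it cuts the standard error by about 12–33% with Poisson noise only and about 7–10% with 10% extra month-to-month variation. The benefit falls mainly on the Implementation 1 comparison. The principal analysis, the system with diversion, is unaffected if the effect is near the pilot's figure of over 68%.

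The size rests on the assumed calendar, proportionality to working days, a 12-month baseline and the assumed volumes. It is not evidence of systematic bias or of an inflated false-positive rate.

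**What to change.** In section XI, keep the monthly number of referrals by destination as the primary outcome and go on reporting and plotting raw counts. Add one sentence: the segmented regression will include the number of working days in each month as a covariate, or log working days as an offset if a count model is used. Where volume drops sharply in Implementation 2, a single additive coefficient is only approximate; the offset form avoids this.

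The term is in addition to seasonal terms for the December/January and March patterns. Those should be few, such as harmonics. With breaks at months 12 and 24, a full set of calendar-month indicators is exactly collinear with the trend and the two steps (rank 16 for 17 columns). With harmonics fitted, little of the working-day benefit is lost.

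The cost is a public calendar, no new data, one degree of freedom and about 2% of the standard error on average. The added assumption is that the recorded month follows weekday working. Reporting the estimated coefficient checks it; if an offset is used, the coefficient should be freed in a sensitivity analysis.

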There is evidence to suggest that the process of collecting, assessing and administratively triaging referrals can result in a decrease of referrals into secondary care. The first twelve months of the intervention will therefore involve practitioners using the electronic referral system, the conditional entry process and the use of administrative and clinical triage. Although the system will capture the decision-making, no primary care diversion will be available and all patients will ultimately be seen in secondary care settings. Referrals that do not meet the threshold will be returned and the case notes system will be in operation enabling advice to be given and further information to be sourced. The system will therefore be operational, but patients will not be diverted to alternate providers. Data from this phase of the study will be used to assess primary care MOS need and applied to assist the procurement of appropriate services based on an AQP (any qualified provider) approach in preparation for the full implementation of the system. In addition, data from this phase will be used to assess the potential activity loss from the acute trust providers.

Implementation 2: Full Referral management with diversion (year 3)

The system will be fully operational and implemented with the use of primary care MOS services.

Outcomes

The primary outcome will be the number and ultimate destination of referrals: rejected, primary care, primary advances or secondary care. There are three main sources of data that will be collected:

- a) Referrals entering acute trusts from dentists via the referral receipt centre of the relevant hospitals
- b) NHS monitoring data received by the local Primary Care Trust and the Payment by Results system including tariff charges associated with this type of activity
- c) Reporting data from NHS business services authority on referrals made by practitioners

This data will be collected continuously, throughout the duration of the study.

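### The primary outcome definition runs the baseline only to six months, contradicting the 12-month baseline elsewhere and leaving months 7 to 12 in no analysis segment

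*Protocol*

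**What the plan says.** The Protocol gives two lengths for the baseline.

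- **Section IX, Study design.** Phase 1 (baseline data, system installation and training) occupies months 1 to 12. The interrupted time series subsection describes an approach "which will involve collection of baseline data over 12 months, followed by staged implementation".
- **Section IX, Outcomes.** Of the three referral data sources it says: "This data will be collected continuously, throughout the duration of the study". Counts for months 7 to 12 will therefore exist.
- **Section XI, Quantitative data analysis.** The primary outcome counts each month's referrals by where they end up. Its time span is given as "from baseline through to six months, implementation stage 1 referral management alone (12 to 24 months"). The stage with diversion then covers months 24 to 36. No reason is given for stopping the baseline at six months.

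The same section estimates the level change by "extrapolating the pre intervention regression line to the first post intervention point" and the slope change by "calculating the post intervention minus pre intervention slope". It does not say which months make up the pre-intervention line. It also defends the uncontrolled design by arguing that "lengthy evaluation pre-intervention and during two stage implementation over three years will address any concerns regarding secular trends".

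**The concern.** Both effect sizes use the pre-intervention line as the counterfactual. If that line is fitted to months 1 to 6 and the first post-intervention point is month 13, it has to be carried across six months in which data were collected but not used. An analyst could follow either passage and obtain materially different precision, and possibly different estimates, for the primary outcome. That choice should not be open once the data can be seen.

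A six-month baseline also weakens the Protocol's own argument that a long pre-intervention period answers concerns about secular trend.

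**Working it through.** The Protocol states no power, sample size or standard error, so there is no figure to reproduce. The check applies the Protocol's own estimator: separate straight lines before and after, differenced at the first post-intervention month.

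**Inputs**
- Pre-intervention months: 1–12 (section IX) or 1–6 (section XI read literally).
- Post-intervention months: 13–24, with the first point at t0 = 13. The Protocol's windows share months 12 and 24; here they are treated as non-overlapping.
- Assumptions: one point per month, equal residual SD (sigma) in both segments, no seasonal terms and, at first, independent errors. Sigma is not given, but it cancels in the ratios.

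**Formulas**
- Variance of a fitted line at t0: sigma² × [1/n + (t0 − mean month)²/Sxx].
- Level-change SE: square root of the sum of the pre and post variances at t0.
- Slope-change SE: sigma × √(1/Sxx_pre + 1/Sxx_post).
- Sxx is 17.5 for six consecutive months and 143 for twelve.

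**Level change at month 13** (variances in sigma²)
- Post line: 1/12 + 5.5²/143 = 0.295.
- Pre line, months 1–12: 1/12 + 6.5²/143 = 0.379. SE = √(0.379 + 0.295) = 0.82 sigma.
- Pre line, months 1–6: 1/6 + 9.5²/17.5 = 5.324. SE = √(5.324 + 0.295) = 2.37 sigma.
- Ratio: about 2.9.

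**Slope change**
- Months 1–12: √(1/143 + 1/143) = 0.118 sigma per month.
- Months 1–6: √(1/17.5 + 1/143) = 0.253 sigma per month.
- Ratio: about 2.1.

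**Gap or number of points?** Six months next to the start (7–12) would give a pre-line variance of 1/6 + 3.5²/17.5 = 0.867 and a level-change SE of √(0.867 + 0.295) = 1.08 sigma, only 1.31 times the 12-month value. The total variance thus goes from 0.674 to 1.162 by halving the points, and from 1.162 to 5.619 by adding the gap. The gap accounts for (5.619 − 1.162)/(5.619 − 0.674) = 90% of the increase.

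**Sensitivity of the level-change ratio (months 1–6 v full baseline)**
- First-order autocorrelation 0.2, 0.4, 0.6: 2.85, 2.90, 3.13. The slope ratio falls to 1.99, 1.80, 1.57.
- Stage 1 starting at month 12 (full baseline then months 1–11): 2.54 to 2.81 over autocorrelation 0 to 0.6.
- Post line fitted to months 13–36: 3.05 to 3.20.

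**Stage 2 (start at month 25)**
- Against the projected baseline line: months 1–6 give 1/6 + 21.5²/17.5 = 26.581, SE √(26.581 + 0.295) = 5.18 sigma. Months 1–12 give 1/12 + 18.5²/143 = 2.477, SE √(2.477 + 0.295) = 1.66 sigma. The ratio is 3.11, falling to 2.42 at autocorrelation 0.6.
- Against the stage 1 line: 0.82 sigma under either baseline, because the baseline does not enter.

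**The case against.** The strongest reply is that the six-month phrase is a drafting slip. It occurs once, in a sentence naming the outcome measure; section IX points to 12 months, and the paragraph that defines the estimator sets no six-month limit. This is plausible, and a reader who infers that the Protocol has settled on discarding half its baseline goes further than the text allows. What stands is that the conflicting phrase sits in the primary outcome definition and nothing in the Protocol says which passage governs.

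Other tempting readings also fail.

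- **That every time series estimate is compromised.** A stage 2 v stage 1 contrast does not use the baseline. The principal analysis concerns the system with diversion, and the text does not settle whether that is judged against stage 1 or against the projected baseline.
- **That six points are in themselves the cause.** The loss comes mainly from the gap.
- **That twelve months would resolve seasonality.** The Protocol notes a fall around December and January and a rise around March. Six months cannot cover that cycle, but a single 12-month cycle does not separate season from trend either. The Protocol relies on 24 months of referral management to measure season and on national hospital data as a check on secular trend.
- **That earlier months could simply be added.** Nothing shows that the routine sources hold earlier monthly counts by the destinations in the primary outcome.

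Installation and training fall in Phase 1, so leaving out some months as a transition period could be legitimate, but the Protocol would have to say so and does not.

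**Conclusion.** The point holds as an internal contradiction with a material consequence if the six-month wording is followed. Section XI and section IX give different baselines, and months 7 to 12 have no place in the primary series. On the literal reading the level-change standard error is about 2.9 times, and the slope-change standard error about 2.1 times, what the planned data would give. The level ratio at month 13 changes little over the autocorrelations tried; the slope ratio declines as autocorrelation rises.

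These ratios rest on straight-line segments, equal residual variance, no seasonal terms and the six months being months 1 to 6. No absolute detectable effect is claimed, because sigma is not given. With six months, the appeal to a long pre-intervention period loses much of its force.

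**What to change.** In section XI, Quantitative data analysis, replace the six-month baseline wording with *baseline (months 1 to 12)* and set non-overlapping segments: months 1–12, 13–24 and 25–36. State that the pre-intervention line is fitted to months 1–12. If installation and training make months 7–12 atypical, say so and examine their exclusion in a sensitivity analysis.

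This is a one-line correction that needs no new data. Earlier retrospective months are optional, worth adding only if the routine sources prove to hold comparable monthly counts; the cost of obtaining them cannot be judged from the Protocol.

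### Autocorrelation is adjusted by maximum likelihood only conditionally; with about 36 months, both test-then-adjust and plain ML would inflate false positives if autocorrelation is moderate

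*Protocol*

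**What the plan says.** In the Protocol, Section XI, under Quantitative data analysis, straight lines before and after each intervention are fitted by linear regression. On serial correlation the section says that "autocorrelation will be adjusted for by using the maximum likelihood methods where appropriate". The text continues: "First order autocorrelations will be tested for statistically using the Durbin – Watson statistic". For higher orders, "autocorrelations will be investigated using the autocorrelation and partial autocorrelation function". A level change and a slope change are to be estimated for each referral destination and examined for statistical significance. The principal question is whether management with diversion has an effect distinguishable from the secular trend.

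The section does not say what makes adjustment appropriate. It gives no significance level or sidedness for the Durbin-Watson test, no expected autocorrelation, and no number of time points.

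**The concern.** At first order, Durbin-Watson is the only stated basis for deciding whether to adjust. If adjustment follows only a significant result, ordinary least squares standard errors are kept whenever the test misses. In a short series with several segments the test misses often. When the adjustment is made, ordinary maximum likelihood underestimates the correlation in so short a series, so the standard errors stay too small.

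The study has no concurrent control, as the protocol acknowledges, so its conclusion leans on the within-series standard errors. Correlated residuals are plausible: Section IX reports falls in referrals around December and January and rises around March. Understated errors would make p-values for level and slope changes too optimistic.

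**Working it through.** The plan states no power, error rate or autocorrelation, so there is no figure of its own to reproduce. The check is a simulation.

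**Inputs from the protocol**
- Baseline: "collection of baseline data over 12 months, followed by staged implementation" (Section IX).
- Implementation: "implementation stage 1 referral management alone (12 to 24 months) and Implementation stage 2, referral management with diversion (24 to 36 months" (Section XI), that is 12 + 12 months.
- Total: 12 + 12 + 12 = 36 monthly points. This is implied, not stated.
- Two breaks with a level and a slope change at each: 2 + 2 × 2 = 6 parameters, leaving 36 − 6 = 30 residual degrees of freedom.

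**Assumptions**
- Stationary AR(1) normal errors with lag-1 correlation ρ from 0 to 0.5.
- No true effect and no seasonal terms.
- Two-sided 5% tests against t(30).
- Durbin-Watson one-sided at 5% with its exact critical value.

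**Model**

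y(t) = b0 + b1·t + b2·I(t>12) + b3·(t−12)₊ + b4·I(t>24) + b5·(t−24)₊ + e(t), with e(t) = ρ·e(t−1) + u(t).

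Durbin-Watson: d = Σ[r(t) − r(t−1)]² / Σ r(t)², where r are the OLS residuals.

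**Results** (false-positive rates; ranges cover level and slope changes and repeat runs)

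| ρ | Durbin-Watson detects | OLS, no correction | Test, then ML | ML always | REML always |
|---|---|---|---|---|---|
| 0 | 5% | 5% | about 5% | about 10% | 6-7% |
| 0.2 | 22% | 9-11% | about 9% | 11-13% | 7-8% |
| 0.3 | 37% | 12-15% | 11-13% | 12-15% | 7-10% |
| 0.4 | 52% | 16-21% | 13-17% | 14-18% | 8-10% |
| 0.5 | 65% | 20-26% | 14-21% | 15-21% | 8-10% |

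The main runs used 8,000 series per ρ. At a rate of 12% the Monte Carlo standard error is √(0.12 × 0.88 / 8000) = 0.0036, so the differences from 5% are not noise.

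As multiples of nominal, test-then-ML is 9/5 = 1.8 at ρ 0.2, 11/5 to 13/5 = 2.2 to 2.6 at 0.3, 13/5 to 17/5 = 2.6 to 3.4 at 0.4, and 14/5 to 21/5 = 2.8 to 4.2 at 0.5.

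**Why the test misses.** Fitting six parameters pulls the residual correlation down. The mean lag-1 residual autocorrelation is −0.166 at ρ 0, 0.034 at ρ 0.3 and 0.151 at ρ 0.5. For the same reason, the usual ACF limits of ±1.96/√36 flag lag 1 in only 4-14% of series at ρ 0.2-0.5. Where Durbin-Watson misses at ρ 0.3, the OLS false-positive rate is 13-16%.

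**Sensitivity**
- Durbin-Watson two-sided: detection is 14%, 27%, 41% and 55% at ρ 0.2, 0.3, 0.4 and 0.5.
- Only values below the tabulated lower bound (1.17) counted: detection is 0.3%, 1%, 3% and 7%.
- Two segments instead of three: test-then-ML gives 8-9% at ρ 0.2, rising to 12-15% at 0.5.
- A six-month baseline, as "The primary outcome measures will be the monthly reported number and ultimate destination of referrals from baseline through to six months" could mean (6 + 12 + 12 = 30 points): 7-10% at ρ 0.2, rising to 12-21% at 0.5.

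**The case against.** The strongest reply is that the rule tested here is not written down. The protocol lists a conditional adjustment and some diagnostics. It never says that a non-significant Durbin-Watson result means OLS, and a plan not shown may define the trigger, the likelihood variant and the reference distribution. Its phrase for the estimator could include restricted maximum likelihood. This stands as a limit: the gate is inferred. It does not remove the point, because the protocol itself names the test, the conditional adjustment and the estimator, and offers no other first-order criterion.

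A reader might infer more than the protocol supports:
- **That Durbin-Watson misses most moderate autocorrelation.** This is true at ρ 0.2-0.3. At 0.4 the exact one-sided test detects about half and at 0.5 about two thirds.
- **That the false-positive rate simply is two to four times nominal.** The protocol gives no ρ. The multiple is under two at 0.2, and the rule holds about 5% at ρ 0.
- **That the test is the culprit.** Always fitting plain ML is no better.
- **That the error rates are higher still.** Judging always-fitted ML against 1.96 gives 16.5% (level) and 21.0% (slope) at ρ 0.3, but the protocol states no normal reference. With t(30) and the residual variance on 30 degrees of freedom, the figures are 12.8% and 14.4%.

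Two further replies have force. The simulation has no seasonal terms, although the protocol expects monthly data to let the cycle be accounted for. And the pilot redirected over 68% of referrals; a level change at diversion near that size would probably not turn on this correction.

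**Conclusion.** The point holds in a conditional form. The protocol makes the autocorrelation adjustment depend on an undefined judgement whose only named first-order test has limited power in a series this short. If ρ is 0.3-0.5, test-then-ML would give roughly two to four times the nominal 5% false-positive rate for the level and slope change at diversion; at 0.2 it would be a little under twice. The conditional rule and plain ML each leave inflation of about this order, so changing one alone is not enough.

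This rests on 36 monthly points in three segments, AR(1) errors, an assumed ρ and the inferred reading of the rule. The consequence falls mainly on slope changes and on the smaller effect of referral management without diversion.

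**What to change.** Replace the conditional adjustment in Section XI with:

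> All segmented models will be fitted with AR(1) errors by REML with t-based inference on residual degrees of freedom (or an equivalent small-sample correction), whatever the Durbin-Watson result; Durbin-Watson, ACF and PACF are diagnostics only.

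The cost is one sentence, standard software and wider confidence intervals. The remedy is partial: the error rate falls to about 7-10% at ρ 0.2-0.5 rather than to 5%. With no autocorrelation it is about 6-7%, slightly worse than the conditional rule's roughly 5%. Borderline p-values should be read with that in mind.
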